3 STUDY OUTCOMES

Primary outcome measure is time to heal in patients treated with epidermal grafting and SOC vs. SOC alone (**Group 1A** versus **Group 2A** at 6 weeks; and **Group 1A** versus **Group 2B** at 12 weeks).

Secondary outcomes include:

1. Percentage of wounds closed at 6 and 12 weeks.
2. Correlation between protease activity and healing at 4 and 8 weeks.
3. Incidence of adverse events at 12 weeks.
4. Pain reduction between baseline and 12 weeks.
5. Cost-effectiveness (see Appendix 19.4)
6. Cost-benefit (see Appendix 19.4)

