The Treatment Phase (TV1 to TV13) Begins with a series of assessments designed to confirm the subjects’ continued eligibility. Investigators will debride the ulcer. Subjects whose ulcers continue to meet eligibility criteria will then be randomized to one of two groups: (1) One application of epidermal microdome at day zero and standard of care (**Group 1A**) OR (2) standard of care: multi-layer compression (**Group 2A**) (see figure on next page).

During the Treatment Phase, subjects will be evaluated on a weekly basis. Effectiveness evaluations each week will include Investigator assessment of wound healing and measurements of ulcer size using digital photos.

At TV 7, wound assessment will be carried out to evaluate wound healing in **Group 2A**. Subjects in **Group 2A**, whose percentage area reduction (PAR) is <40% will be allowed to have CelluTome™ treatment in addition to continuation of SOC and will constitute **Group 2C**. **Group 2C** will receive a graft at TV7 and TV11. The remainder of **Group 2A** subjects will be termed **Group 2B** subjects. Patient codes will still remain the same to enable tracking continuity.

[figure not shown]
During the Treatment Phase, the wound will be swabbed for protease activity for **Group 1A and 2A/B** subjects: TV1 (In **Group 1A** this will be prior to CelluTome™ application), TV5 and TV9 visits.

Subjects will be evaluated on a weekly basis during the Treatment Phase. Effectiveness evaluations each week will include Investigator assessment of wound healing and measurements of ulcer size using digital planimetry. At TV4 and TV8, Prisma™ is to be applied to the study ulcer for **Groups 1A, 2A, and 2B** subjects. **Group 2C** subjects will receive Prisma™ at TV10. Safety evaluations during the Treatment

CELLUTOME™ IN VENOUS LEG

Phase will consist of adverse event assessments at each visit.

Diagram showing progress of trial and the different subjects groups. Up to 6 weeks from randomization only **Groups 1A and 2A** exist; after 6 weeks, **Groups 1A, 2B, and 2C** exist.

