5 STUDY POPULATION

5.1 NUMBER OF SUBJECTS

The study will consist of up to 30 centers in the United States each contributing about 10 subjects per center in order to obtain 300 evaluable subjects. We anticipate a 10% drop out rate during the trial for both Groups 1A and Group 2A, and 30% of subjects in Group 2A will switch to Group 2C and therefore a total of 225 subjects will be recruited. This trial employs an adaptive design therefore the enrollment numbers may be reduced or increased based on planned interim analysis.

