6.1 VISIT WINDOWS

Subject visit dates must be scheduled within the visit windows detailed on the Schedule of Events tables. One week equals 7 days.

During the Screening Phase, each visit is scheduled from the S1 visit date, with reference to the allowed visit window.

During the Treatment Phase, each visit is scheduled from the TV1 visit date, with reference to the allowed visit window. For example, the TV2 visit is scheduled for 1 week \pm 2 days after the TV1 visit. TV3 is scheduled for 2 weeks \pm 2 days after the TV1 visit.

SCHEDULE OF EVENTS

Visit	SVs (14 days)	TV1 (rand)	T V	TV3	TV4	TV5	TV6	TV7	TV8	TV9	TV10	TV11	TV12- 13
Weeks from Randomization Date			+1	+2	+3	+4	+5	+6	+7	+8	+9	+10	+11-12
Window Period	0		±2 da	±2 days	±2 days	±2 days	±2 days	±2 day	±2 days	±2 days	±2 days	±2 days	±2 days
Assessment of eligibility	√												
Medical history	√												
Apply Prisma™	√				√				√		√ ^[B]		
Randomization		√											
Ulcer assessments	√		√	√	√	√	√	√	√	√	√	√	√
Physical exam	√												
Vital signs	√												
Pain assessment	√		√	√	√	√	√	√	√	√	√	√	√
Study ulcer photographs	√		√	√	√	√	√	√	√	√	√	√	√
Study ulcer cleaning	√		√	√	√	√	√	√	√	√	√	√	√
Study ulcer debridement	√ ^[A]		√	√	√	√	√	√	√	√	√	√	√
Study ulcer swab	√	√				√				√			
Assessment of compression bandaging	√		√	√	√	√	√	√	√	√	√	√	√
Epidermal graft application		√				√		√ ^[B]		√		√ ^[B]	
Study ulcer dressings and compression therapy	√	√	√	√	√	√	√	√	√	√	√	√	√
Study ulcer closure assessment			√	√	√	√	√	√ ^[C]	√	√	√	√	√
Assess for concomitant medications	√	√	√	√	√	√	√	√	√	√	√	√	√
Assess for AEs and SAEs		√	√	√	√	√	√	√	√	√	√	√	√
Quality of Life, PBI-P and Time-trade off questionnaires		√				√				√			√ ^[D]

[A] – If required per the Investigator’s judgment.

[B] – **Group 2C** subjects only

[C] – Evaluation of wound area reduction since TV1. Subjects in **Group 2A** (SOC), whose study ulcer PAR is < 40%, will become **Group 2C**; the remainder of **Group 2A** subjects will become **Group 2B**

[D]- Questionnaires are to be completed for TV13 only

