9.2 RESEARCH HYPOTHESES

Primary endpoints

H1: Time to heal

Time to heal after 12 weeks of CelluTome™ + SOC (**Group 1A**; maximum of 3 CelluTome™ applications) versus 12 weeks of SOC (**Group 2B**) will be equal for both groups or time to heal after 6 weeks of CelluTome™ + SOC (**Group 1A**; maximum of 2 CelluTome™ applications) versus 6 weeks of SOC (**Group 2A**) will be equal for both groups. Formally, $H_0: T_1 - T_2 = 0$; $H_A: T_1 - T_2 = D_1 \neq 0$, where T_1 is the time to heal for **Group 1A**, T_2 is the time to heal for **Group 2A or 2B** depending whether T_2 is 12 or 6 weeks, D_1 is the difference ($T_1 - T_2$) assuming the alternative hypothesis, and statistical test used is log rank applied to a Kaplan-Meier analysis. If either result is statistically significant, results will be adjusted using Cox regression and appropriate covariates.

Secondary endpoints

H2: Proportion of wounds healed

The proportion of wounds healed at 12 weeks after 12 weeks of CelluTome™ + SOC (**Group 1A**; maximum of 3 CelluTome™ applications) versus 12 weeks of SOC (**Group 2B**) will be equal for both groups. Formally, $H_0: P_1 - P_2 = 0$; $H_A: P_1 - P_2 = D_1 \neq 0$, where P_1 is the proportion of wounds healed for **Group 1A**, P_2 is the proportion of wounds healed for **Group 2B**, D_1 is the difference ($P_1 - P_2$) assuming the alternative hypothesis, and statistical test used is chi square.

H3: Incidence of Adverse Events (AEs)

The incidence of adverse events (AEs) by 12 weeks after 12 weeks of CelluTome™ + SOC (**Group 1A**; maximum of 3 CelluTome™ applications) versus 12 weeks of SOC (**Group 2B**) will be equal for both groups. Formally, $H_0: I_1 - I_2 = 0$; $H_A: I_1 - I_2 = D_1 \neq 0$, where I_1 is the incidence of AEs for **Group 1A** on a per subject basis, I_2 is same metric for **Group 2B**, D_1 is the difference ($I_1 - I_2$) assuming the alternative hypothesis, and statistical test used is the Mann-Whitney test.

H4: Correlation of wound area with protease activity at 4 weeks

The Pearson correlation coefficient (or Spearman's rho in the case of severe non-normality) calculated

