9.3 SAMPLE SIZE CALCULATIONS

A two-sided logrank test with an overall sample size of 225 subjects (113 in the control group and 112 in the treatment group) achieves 86.1% power at a 0.05 significance level to detect a hazard ratio of 1.74 when the proportion of wounds healed in the control group is 0.5. The study lasts for 12 weeks with all subjects beginning the study together (no accrual periods). The proportion dropping out of the control group is 0.033 per week. The proportion dropping out of the treatment group is 0.0083 per week. The proportion switching from the control group to another group with a hazard ratio equal to that of the treatment group is 0.

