9.7 STATISTICAL METHODS

MISSING DATA

Missing data may be the result of missed visits, subjects lost to follow-up or who have died, or data not available (e.g., smoking status).

Missing primary endpoint data within 12 weeks from start of study will not be imputed for ITT populations as these will constitute right-censored data in the time to heal analysis. The last visit for which data are available will constitute the start of censoring (healing outcome). For secondary endpoints within 12 weeks from start of study, the last observation carried forward (LOCF) principle will be used for ITT populations.

For adjusted analyses of primary and secondary endpoints, missing data for covariates used to adjust analyses may be imputed in separate models when the missing data for each covariate is $\leq 30\%$ and it can be reasonably demonstrated that the missing data for each covariate are MCAR.

FINAL ANALYSIS

Analysis can be started when database lock for the trial is initiated. In regard to statistical modeling, the initial list of independent variables will be examined for correlation between pairs. In the event that

correlation (however calculated) exceeds 0.7, a selection will be made between the 2 variables to avoid possible issues of co linearity and variance inflation.

The following analysis will be conducted:

1. Flow chart (subjects)
2. Overall trial statistics (enrollment dates, site numbers, numbers of subjects)
3. Demographics between groups at baseline (no statistical testing but identification of likely trial imbalances)
4. Count of subjects in each group
5. Primary endpoints within 6 and 12 weeks (time to heal; previously defined by groups) will be analyzed by Kaplan-Meier and log rank test (unadjusted); and then Cox regression to adjust for the following variables (with and without covariate imputation):

- Site
- Year enrolled (if trial lasts 2 years or more)
- Treatment group
- Initial area at randomization (cm²)
- Initial wound depth (cm)
- Age of wound at enrollment (days)
- Smoking status
- Prior VLU
- Pain score at randomization
- Patient age
- Gender
- Ethnicity/race
- VCS score
- Diabetes
- Patient on pain medications
- Smoking status
- BMI
- Infection episodes

6. Secondary endpoints will be analyzed as follows:

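### The 12-week primary comparison sets the whole graft arm against a control group stripped of its slow healers

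*Combined protocol and SAP*

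**What the plan says.** Section 3 gives two primary comparisons of time to heal: 1A against 2A at 6 weeks, "and Group 1A versus Group 2B at 12 weeks". H1 in section 9.2 repeats this: time to heal on 12 weeks of graft plus SOC "versus 12 weeks of SOC (Group 2B) will be equal for both groups". H2 (proportion healed), H3 (adverse events), H5 (week-8 protease correlation) and H6 (pain) also take 2B as control. H7 and H8 compare 2C with 2B.

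Group 2B is formed at TV7 (week 6). Footnote C of the Schedule of Events (6.1) says SOC subjects "whose study ulcer PAR is < 40%, will become Group 2C; the remainder of Group 2A subjects will become Group 2B". Section 4 agrees: "The remainder of Group 2A subjects will be termed Group 2B subjects". It also says that after week 6 the groups are 1A, 2B and 2C, so 1A stays whole.

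Section 5.1 expects 10% dropout in each arm and that "30% of subjects in Group 2A will switch to Group 2C". In section 9.3, "The proportion dropping out of the control group is 0.033 per week", against 0.0083 in the treatment group. The same section adds: "The proportion switching from the control group to another group with a hazard ratio equal to that of the treatment group is 0". Section 9.7 does not impute missing primary data, "as these will constitute right-censored data in the time to heal analysis", and has no rule for switchers. Section 9.6 names an ITT population but does not define it as all randomised subjects by assigned arm.

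**The concern.** Randomisation makes 1A comparable with 2A, not with 2B. Subjects leave the control group because of an early form of the outcome itself, while equally slow healers in 1A are kept. No specified analysis compares 1A with all of 2A at 12 weeks, and the Cox covariates in 9.7 do not include week-6 area reduction. Adjusting for a response applied as a filter in one arm would not restore the comparison anyway.

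Two things are at stake. A real graft benefit could be hidden at 12 weeks, and an ineffective graft could appear harmful to healing. The stated power belongs to this comparison, and it treats removal for slow healing as loss at random.

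**Working it through.** **1. The plan's power figure.** Section 9.3 inputs: 113 control and 112 treatment subjects, 12 weeks, control healing 0.5, hazard ratio 1.74, dropout 0.033 and 0.0083 per week. With exponential healing:

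- Control: healing hazard ln 2/12 = 0.0578, dropout hazard −ln(1 − 0.033) = 0.0336. P(event) = 0.0578/0.0913 × (1 − e^(−12 × 0.0913)) = 0.421, so 47.6 events.
- Treatment: healing hazard 0.1005, dropout hazard 0.0083. P(event) = 0.673, so 75.4 events.
- Total 123 events. Schoenfeld: ln 1.74 × √(123/4) − 1.96 = 3.07 − 1.96 = 1.11, power 86.7%. A finely stepped Markov log-rank calculation gives 85.7%.

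The stated 86.1% reproduces. The control dropout rate is 0.033 × 12 ≈ 40%, which equals section 5.1's 10% dropout plus 30% switching. The treatment rate is 0.0083 × 12 ≈ 10%. The calculation therefore counts switchers as uninformative dropouts, with crossover set to 0.

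**2. What selection does to control healing.** Let q be the share of switchers who would heal on SOC alone by week 12. The documents do not give q. Under the plan's model, SOC healing by week 6 is 1 − √0.5 = 0.293, leaving 0.707 unhealed. An average unhealed subject then heals by week 12 with probability 0.293. So q = 0.293 means that area reduction below 40% predicts nothing beyond being unhealed, and q = 0 means no switcher would have healed.

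- 2C excluded: 2B healing = (0.5 − 0.3q)/0.7.
- 2C censored at week 6: the 0.407 who are unhealed and do not switch stand in for all 0.707. Estimated healing = 1 − 0.707 × [1 − (0.207 − 0.3q)/0.407], where 0.207 = 0.5 − 0.293.

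For comparison, 1A heals 1 − 0.5^1.74 = 70.1% at hazard ratio 1.74, and 50% with no effect.

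**3. What that does to the test.** Log-rank simulation, 10,000 trials per cell: 112 and 113 subjects, random dropout 0.0083 per week in both arms, 30% of 2A switching at week 6, all unhealed then. *Power* is the chance of showing benefit at hazard ratio 1.74. *False worse* is the chance that the graft is significantly worse when there is no effect.

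| q | 0 | 0.1 | 0.2 | 0.293 |
|---|---|---|---|---|
| Excluded: control healing | 71% | 67% | 63% | 59% |
| Excluded: power | 3% | 7% | 15% | 27% |
| Excluded: false worse | 81% | 65% | 47% | 31% |
| Censored: control healing | 65% | 60% | 55% | 50% |
| Censored: power | 39% | 57% | 73% | 85% |
| Censored: false worse | 30% | 15% | 6% | 3% |

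Modelling details, such as rounding healing times to weekly visits, move these figures by a few points.

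**4. Randomised alternatives.** With no true effect, all of 2A analysed as randomised gives 2.3–2.6% error in each direction, and so does the 6-week test. At 6 weeks, with dropout 0.0083 in both arms, about 82 events are expected: ln 1.74 × √(82/4) − 1.96 = 0.55, power about 71%. The Markov calculation gives 70%, and 86.2% with 340 subjects.

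**The case against.** The best defence is that the bias is conservative. The trial seeks superiority, the selection does not inflate false claims of benefit, and H1 acts on either result, so the valid 6-week test remains. This limits the harm. It does not repair a named primary endpoint, and a hidden benefit or a false finding of harm is still an error.

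Second, the size depends on the reading. Under censoring, which section 9.3 implies, the excess error is small at q = 0.2 and gone at 0.293, and the direction requires area reduction below 40% to predict slower healing. That is plausible, but it is an assumption. Under exclusion no such assumption is needed, because only open ulcers can be removed.

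Third, direction and size are shown only for healing (H1 and H2). For adverse events, correlation and pain, the comparison is selected but the direction is not established.

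Fourth, analysing all of 2A at 12 weeks changes the question: it compares early grafting with SOC plus delayed grafting for poor responders. Power can fall to 38%, no better than the biased censored analysis at q = 0. The gain is error control, and the plan should say so.

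These points narrow the claim. None makes 1A against 2B a randomised comparison.

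**Conclusion.** The concern holds. The 12-week primary comparison uses a control group selected after randomisation, on outcome, in one arm only, and nothing in 9.3, 9.6 or 9.7 corrects it. For healing, the bias runs against the graft: always if 2C is excluded, and if 2C is censored whenever poor week-6 area reduction predicts slower healing. The magnitudes in the table rest on exponential healing, 30% switching, the assumed q, and which handling applies. The 86.1% reproduces arithmetically but does not describe the comparison as H1 words it. The 6-week comparison of 1A with 2A is sound. This must be fixed before analysis.

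**What to change.** - **Section 3, H1, H2 and H6:** replace 2B with all subjects randomised to SOC (2A = 2B + 2C), analysed as randomised, with outcomes counted as observed after crossover. State that the 12-week contrast includes delayed grafting in the control arm.
- **Primary:** keep 1A against 2A through TV7 as the comparison free of crossover.
- **Section 9.6:** define ITT as all randomised subjects by assigned arm.
- **H3:** compare adverse events as randomised up to TV7, then report later events by treatment received (1A, 2B, 2C). Other splits are possible, but graft and donor-site events in 2C should not count as control events.
- **H5:** label it descriptive. Also reconcile the swab rule: the synopsis and section 4 limit treatment-phase swabs to 1A and 2A/B, while the Schedule of Events and the TV5/TV9 procedures set no group limit.
- **H7 and H8:** label them non-randomised comparisons.
- **Crossover rule:** this change does not touch it.

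No new data are needed: 2C subjects are followed weekly to TV13, and adverse event onset dates are already collected.

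The cost is power, so section 9.3 must be recalculated. At 225 subjects and two-sided 0.05, 6-week power is about 70%; about 340 subjects would give 86%. At 12 weeks, as randomised, power is 88% if grafting does nothing for switchers, about 71–88% if it speeds their own SOC healing by 1.74 (depending on q and how this is modelled), and 38–75% if they heal at the full 1A rate after week 6. A flat 0.025 for the 6-week test would give about 59%. That is the worst case under the Hochberg procedure in 9.7, which rejects both primary hypotheses when both p-values are at most 0.05.

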4 STUDY DESIGN

This study is a multi-center, randomized, controlled open-label study designed to evaluate the safety and effectiveness of epidermal grafting using the CelluTome™ system plus SOC (multi-layer compression) versus SOC alone in the treatment of VLUs.

The study will have two phases: Screening and Treatment.

The Screening Phase (1 -14 days) is designed to determine whether subjects are eligible to proceed to the Treatment Phase of the study and consists of a series of screening assessments designed to determine eligibility.

At or up to 14 days before the first Screening Phase Visit (S1), written informed consent from the subject will be obtained by the Investigator or suitably qualified designee before the performance of any other protocol-specific procedure.

At the first Screening Phase Visit (S1), the Investigator will select the study (target) ulcer. Each subject will have only one VLU selected as the study (target) ulcer. In the situation where a subject has more than one VLU at the S1 visit, the Investigator will select the largest VLU that meets the eligibility criteria of the protocol as the study (target) ulcer.

The wound will be swabbed for protease activity to measure the absolute values of inflammatory proteases (Neutrophil elastase, MMP 8 and 9) before the application of Prisma™ Matrix Wound Dressing (Systagenix, San Antonio, TX).

Prisma™ is to be used during the 2 week screening phase. Prisma™ provides a moist environment at the wound surface and provides an effective barrier against common pathogens. The rationale for permitting the use of Prisma™ in subjects is to reduce the risk of infection. For subjects who are allergic to Prisma™, any of the allowed antimicrobial dressings should be used (see Appendix 19.8).

Patients whose target ulcer has been treated with compression therapy for the previous two weeks are eligible to enter the treatment phase once all of the inclusion and exclusion criteria are met. If the ulcer has not received compression, the patient should be placed in compression and enrolled in the study after 14 days of compression therapy. Ulcers that have decreased in size by more than 40% during the screening period will be excluded as a “rapid healer.”

The Treatment Phase (TV1 to TV13) Begins with a series of assessments designed to confirm the subjects’ continued eligibility. Investigators will debride the ulcer. Subjects whose ulcers continue to meet eligibility criteria will then be randomized to one of two groups: (1) One application of epidermal microdome at day zero and standard of care (**Group 1A**) OR (2) standard of care: multi-layer compression (**Group 2A**) (see figure on next page).

During the Treatment Phase, subjects will be evaluated on a weekly basis. Effectiveness evaluations each week will include Investigator assessment of wound healing and measurements of ulcer size using digital photos.

At TV 7, wound assessment will be carried out to evaluate wound healing in **Group 2A**. Subjects in **Group 2A**, whose percentage area reduction (PAR) is <40% will be allowed to have CelluTome™ treatment in addition to continuation of SOC and will constitute **Group 2C**. **Group 2C** will receive a graft at TV7 and TV11. The remainder of **Group 2A** subjects will be termed **Group 2B** subjects. Patient codes will still remain the same to enable tracking continuity.

[figure not shown]
During the Treatment Phase, the wound will be swabbed for protease activity for **Group 1A and 2A/B** subjects: TV1 (In **Group 1A** this will be prior to CelluTome™ application), TV5 and TV9 visits.

Subjects will be evaluated on a weekly basis during the Treatment Phase. Effectiveness evaluations each week will include Investigator assessment of wound healing and measurements of ulcer size using digital planimetry. At TV4 and TV8, Prisma™ is to be applied to the study ulcer for **Groups 1A, 2A, and 2B** subjects. **Group 2C** subjects will receive Prisma™ at TV10. Safety evaluations during the Treatment

CELLUTOME™ IN VENOUS LEG

Phase will consist of adverse event assessments at each visit.

Diagram showing progress of trial and the different subjects groups. Up to 6 weeks from randomization only **Groups 1A and 2A** exist; after 6 weeks, **Groups 1A, 2B, and 2C** exist.

5 STUDY POPULATION

5.1 NUMBER OF SUBJECTS

The study will consist of up to 30 centers in the United States each contributing about 10 subjects per center in order to obtain 300 evaluable subjects. We anticipate a 10% drop out rate during the trial for both Groups 1A and Group 2A, and 30% of subjects in Group 2A will switch to Group 2C and therefore a total of 225 subjects will be recruited. This trial employs an adaptive design therefore the enrollment numbers may be reduced or increased based on planned interim analysis.

